### *2.2.1 Inclusion criteria*

- Cis female experiencing sexual distress with a history of sexual trauma
- Willingness to complete guided self help
- Aged 18 and above
- Ability to read English to provide consent and meaningfully engage with the self-help materials
- Ability to access online guided self-help material through a computer or phone
- Not currently experiencing severe acute mental health problems
- Not currently suicidal or self-harming

### *2.2.2 Exclusion criteria*

Participants will be excluded if they are experiencing severe acute mental health difficulties, sexual assault occurring within the last 12 months or currently experiencing more than fleeting suicidal thoughts or engaging in severe self-harming (individuals who have been sexually assaulted are likely to experience suicidal thoughts or self-harm behaviours, individuals with fleeting suicidal thoughts or superficial self-harm with strong protective factors may be

included however, since there is no contact with mental health professionals during the intervention unless participants reach out for triage, it is difficult to assess risk and participants have to be excluded if they do not have social support systems or are currently accessing psychological support).

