Should individuals wish to participate they will be invited to follow a link to a Qualtrics survey to initial screening questions to check for eligibility. Prior to completing the screening questionnaire participants will be provided the following text 'Thank you for being interested in this study. The next step is to complete a screening questionnaire. This questionnaire aims to determine if this study would be appropriate for you. The questionnaire does not ask you direct questions about your experience of sexual assault; however, it could potentially elicit difficult emotions. Please keep this in mind if you decide to proceed with the questionnaire as your wellbeing is a priority. There are no consequences if you decide to opt out of participating in this study. At the end of the questionnaire, we have included the chief investigator's email along with signposting information about services you can contact if you require additional support. Thank you for your time.' These questions will confirm if participants are experiencing difficulties with sex, have been sexually assaulted over 12 months ago, if they are currently receiving other forms of psychological intervention and have access to a smart phone or computer to access materials. The Patient Health Questionnaire 2-item (PHQ-2) and Generalised Anxiety Disorder 2-item (GAD-2) are incorporated in the screening questionnaire not to screen for depression and/or anxiety but provide an indication of participant demographic. There will also be a risk screen based on the PHQ-9 "Over the past two weeks,

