how often have you been bothered by thoughts that you would be better off dead or of hurting yourself in some way?" - Not at all, Several days, More than half of the days, Nearly every day and a question about support from family and friends. Those who rate themselves as experiencing thoughts of death or self-harm and do not indicate that they have social support or psychological support will not be eligible to participate (see section. Those ineligible to participate will be redirected to a debrief page, 'debrief page for Qualtrics', which will include an explanation of why this is the case and signposting to relevant resources. They will also be provided with the chief investigators email or given the option to leave their telephone number for the chief investigator to call them and discuss why they were not appropriate for the study. Eligible participants will provide informed consent by reading statements relating to the study information and writing their initials if they consent to each statement. This includes confirming they have read the information, understanding participation is voluntary and being able to withdraw from the research at any time. Participants are asked to provide their GP details as part of informed consent. Participants will be informed that their GP will not be notified about their involvement in the study or provided any information contributed whilst participating. We will only contact their GP if there are identified risks. These risks include increased self-harm behaviour, increased suicidal risk or significant deterioration of mental health. Under these circumstances, confidentiality may be breached and, the chief investigator may contact the participants GP. As there is little to no professional contact as part of the study design, the chief investigator will only be made aware of increased risk if the participant raises it to the chief investigator by email.

Eligible participants who provide informed consent will have a screening call with the lead investigator, [name] to verify risk, confirm consent and answer any additional questions about the study. As the intervention is online, we hope that having a call at the

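### Section 2.2.2 as printed excludes at-risk women for having psychological support, and the self-harm and GP rules contradict each other between sections

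*Combined protocol and SAP*

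**What the plan says.** All references are to the Combined protocol and SAP.

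**Support rule.** Section 2.2.2 excludes women who are "currently experiencing more than fleeting suicidal thoughts or engaging in severe self-harming". It then makes an allowance: "individuals with fleeting suicidal thoughts or superficial self-harm with strong protective factors may be" included. The limit on that allowance follows in the same sentence. Because there is no professional contact during the intervention unless a participant asks for triage, "participants have to be excluded if they do not have social support systems or are currently accessing psychological support".

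Section 2.2 gives the rule for the online screen: women who report thoughts of death or self-harm and "do not indicate that they have social support or psychological support will not be eligible to participate". Section 3.4 excludes women who disclose high risk if they are not under mental health services. Section 2.2 also asks, among the screening questions, "if they are currently receiving other forms of psychological intervention", but does not say what follows from a yes. Current and past therapy are then recorded on the demographic sheet, which is completed after the screening call.

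**Self-harm.** The last inclusion bullet in section 2.2.1 requires that a woman is not at present suicidal or self-harming, with no qualification.

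**GP.** Section 2.2 collects GP details as part of consent and states: "Participants will be informed that their GP will not be notified about their involvement in the study". Section 3.4 makes those details a requirement and repeats that the GP is not told. Further on, section 3.4 says participants can give details of a GP, who may be told of their participation, and adds that this is optional. Section 4 relies on the GP for escalation: if concern about risk remains after a 1:1 session with a clinician, the GP is emailed urgently and telephoned.

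**The concern.** An exclusion criterion should give the person applying it one answer. Here it gives the reverse of the plan's own reasoning. Section 2.2.2 worries that nobody in the study is watching these women, and that worry makes sense only if outside support counts in a woman's favour. The printed clause counts it against her.

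The stake is participant safety and fair access, not inference. After entry, section 2.2 says that "the chief investigator will only be made aware of increased risk if the participant raises it to the chief investigator by email". Entry is therefore the main point at which the study itself looks at risk. The screening call, held "to verify risk, confirm consent and answer any additional questions about the study", is a real safeguard, but the caller needs one rule to apply. On the GP, the question is whether the escalation route in section 4 can always be used.

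**Working it through.** The plan gives no figure on this point, so there is nothing to reproduce. The check sets the rules side by side.

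**1. Support rule.** Take a woman with fleeting suicidal thoughts or superficial self-harm. Code social support and current psychological support as yes or no, which gives 2 × 2 = 4 combinations.

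- Section 2.2 screen: removed if she has neither support.
- Section 2.2.2 as printed: removed if she has no social support, or if she is in psychological support. The second verb is a fresh 'are', so grammatically the earlier 'do not' does not carry over to it.
- Section 2.2.2 with the missing negation restored as 'neither': removed if she has neither support.

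| Social | Psychological | 2.2 screen | 2.2.2 as printed | 2.2.2 as 'neither' |
|---|---|---|---|---|
| yes | yes | not removed | removed | not removed |
| yes | no | not removed | not removed | not removed |
| no | yes | not removed | removed | not removed |
| no | no | removed | removed | removed |
| **Removed** | | **1 of 4** | **3 of 4** | **1 of 4** |

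The screen and the printed criterion disagree in 2 of 4 combinations (yes/yes and no/yes), and these are all the combinations with therapy. With 'neither', they agree in 4 of 4. Not being removed by this test is not the same as being admitted, because the other criteria and the screening call still apply.

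Three places show which way the plan leans. The section 2.2 screen lets psychological support keep a woman in. Section 3.4 excludes high-risk women only when they are outside services. The demographic sheet, completed after the call, expects some women to be in therapy.

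**2. Self-harm.** Take a woman with superficial self-harm and strong protective factors. Under section 2.2.2 she may be included. Under the last bullet of section 2.2.1 she fails an inclusion criterion. Entry criteria apply together, so section 2.2.1 prevails and the allowance in section 2.2.2 has no effect for her. Correcting the support clause alone would leave that unchanged.

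**3. GP.** The optional element in the later sentence of section 3.4 has two readings.

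| Reading | Against the rest of the plan | Effect on section 4 escalation |
|---|---|---|
| Giving GP details is optional | Conflicts with the requirement earlier in section 3.4 | Cannot be carried out for a woman who withholds them |
| Telling the GP of participation is optional | Conflicts with sections 2.2 and 3.4, which say the GP is not told | None: details are still held |

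Both readings conflict with other text. Only the first opens a gap in escalation.

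**The case against.** **It is a slip that any reader would correct.** Probably so. If the negation is carried across both halves of the clause, section 2.2.2 agrees with section 2.2 everywhere, so the count of three in four measures a reading the authors are unlikely to have meant. But section 2.2 lists current psychological intervention among its screening questions, alongside the timing of the assault and access to a device, and gives no consequence. A reader could take section 2.2.2 as a deliberate bar on concurrent therapy. The rest of the plan points the other way, but the investigator should confirm it.

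**The strict criterion is the safe one.** On self-harm this is right: applied cumulatively, section 2.2.1 leads to cautious exclusion. What stands is that section 2.2.2 deliberately explains an allowance that section 2.2.1 then makes empty.

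**There are other safeguards.** Ineligible women receive an explanation, signposting and the offer of a call. Enrolled women have crisis signposting with each session and access to clinician triage, which section 4 places before GP contact. These soften the consequences but do not tell the screener which rule to apply.

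**Stronger readings that do not hold.** A reader might infer that sections 2.2 and 3.4 let in women with more than fleeting suicidal thoughts so long as they have support. Section 2.2.2 excludes such women outright, and section 3.4 also removes a high-risk woman whose only support is social, since she is not in services. A reader might also infer that participants are told two different things about their GP. Only section 2.2 states what they will be told. The later sentence in section 3.4 is protocol narrative, and the information sheet is not among the documents.

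**Conclusion.** The point stands as a contradiction in operative eligibility and safety wording, and it should be corrected. Followed literally, section 2.2.2 turns away at-risk women because they are in therapy: 3 of 4 support combinations removed against 1 of 4 under section 2.2, with the difference confined to women in therapy. Section 2.2.1 nullifies the allowance for superficial self-harm. The later GP sentence in section 3.4 conflicts with sections 2.2 and 3.4, and on one of its two readings it leaves section 4 escalation unworkable for a woman who withholds her GP's details.

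This rests on two assumptions: that the support wording in section 2.2 means having neither kind, and that concurrent therapy was not intended as an exclusion.

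The counts are of combinations, not of women. A reader might take the recruitment figures, a target of 20 with a minimum of 6, as the number affected. Exclusion rules act on women screened, and the plan gives no number for those. No statistical result changes.

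**What to change.** First, the investigator confirms that concurrent therapy is not meant as an exclusion, and section 2.2 states how the screening answer on current psychological intervention is used. Then:

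1. Reword section 2.2.2 so that women with fleeting suicidal thoughts or superficial self-harm may be included only with strong protective factors, and are excluded if they have neither social support nor current psychological support.
2. Change the last bullet of section 2.2.1 to match: no more than fleeting suicidal thoughts and no severe self-harm.
3. Delete the later GP sentence in section 3.4, so that the earlier text governs: details are required at consent, the GP is not told of participation, and contact is made only for identified risk.

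A cross-reference to section 2.2.2 from the risk rules in sections 2.2 and 3.4 would help but is optional.

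The cost is a few sentences in the plan, and in the information sheet and the Qualtrics screen if they repeat the wording. It needs no extra participants, visits or data. GP details are already required, so participants face no new demand.

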#### *2.2.3 Criteria for premature withdrawal*

Participants will be able to withdraw from the study at any point by informing the chief investigator

### **2.3 Material provided to participants.**

#### *2.3.1 Intervention*

[figure not shown]
4 Sessions of guided self-help will be shared with the participants. These will be in the form of handout and video recordings that participant access through Qualtrics. The intervention is based on research on sexual trauma, psychosexual difficulties and materials developed by Bart's NHS Foundation Trust Sexual Wellbeing Service. It has been made in collaboration with clinicians within the service, experts by experience and the chief investigator. The intervention handout and scripts is in the document titled 'Intervention Manual V1'. Within the document there are scripts for each session which are read out in the video recordings. The handouts depict the visual images for the video and the materials provided to participant. Additional handouts for each session can be found in the appendix.

#### *2.3.2 Visual Analogue Scales*

Visual analogue scales are to be completed by participants. Visual analogue scales are scales with two ends where participants will be asked to rate how much they agree or disagree with the following statements as seen in figure 1 below:

- **Shame**
  - I feel shame when I experience sexual distress
- **Guilt**
  - I have feelings of guilt when I experience sexual distress
- **Self-criticism**
  - When I experience sexual distress, how often do I blame myself or my body?
- **Compassion**
  - When I experience sexual distress, I try to show myself warmth and comfort through my difficulties
- **Normalising**
  - I understand my difficulties in the context of my experience
- **Motivation**
  - I am motivated to put things in place to improve/ address the difficulties in my sex life

Figure 1: VAS Example

#### *2.3.3 Female Sexual Distress scale – Revised (FSDS-R; Derogatis et al., 2002)*

The FSDS-R is used to assess distress related to sex in women (Derogatis et al., 2002). This 13-item self-report questionnaire is scored has four points, (0: never; 1: rarely; 2: occasionally; 3: frequently). In multiple studies involving more than 500 women, the FSDS-R has shown

high internal consistency (Dergostis et al., 2008) for women with and without sexual difficulties. A validation study demonstrate that the measure has discriminant and content validity (Dergostis et al., 2008). The FSDS-R is completed upon recruitment and at the 1 month follow up.

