## **2. Methods**

### **2.1 Study design**

The study adopts a single-case experimental design (SCED). This study design is helpful in testing the novelty and feasibility of an intervention.

Potential participants will be invited to follow a link to a Qualtrics survey. The Qualtrics survey provides detailed information about the study. Participants will undergo screening for eligibility and risk via Qualtrics. Should individuals wish to participate and are eligible, they can give informed consent by reading a set of statements on Qualtrics relating to the study

information. Eligible participants will fill in questionnaires such as the FSDI, FSFI, SCSS-S, at this point. Participants will undergo a baseline period known as phase A, varying between 5- 14 days where they will fill in visual analogue scales daily. The number of days participants will be in baseline will be randomly allocated by a randomiser. There are 6 visual analogue scales measuring shame, guilt, self-criticism, self-compassion, normalising and motivation. After phase A, participants will undergo phase B, which is a 4-week intervention period where participants go through 1 module of the guided-self-help materials each week and complete the same visual analogue scales from baseline every day. After phase B, participants will be invited for a follow-up appointment one month after the intervention to fill in the FSDS, FSFI, client satisfaction questionnaire (Larsen et al., 1979) and feedback form developed with experts by experience.

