#### *2.3.4 Female Sexual Function Index (FSFI; Rosen et al., 2000)*

The FSFI is a 19-item questionnaire that measures six domains: desire, arousal, lubrication, orgasm, satisfaction and pain. The questionnaire has been used in different clinical trials and epidemiological studies and have shown to have high test-rested reliability and validity, it is scored from 1 to 5 with different response options. The FSFI is completed upon recruitment and at the 1 month follow up.

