#### *2.3.5 State Self Compassion Questionnaire (SSCS-S; Neff et al., 2021)*

The SSCS-S is a 6-item questionnaire scored on a 5-point scale from 1 (not very true for me) to 5 (very true for me). In one study, Neff et al (2021) reports the SSCS-S had a strong correlation ( $r=.96$ ) to the long version of the state self-compassion questionnaire and showed good reliability ( $\alpha = .86$ ). Another study found strong construct validity. The SCSS-S is completed upon recruitment and at the 1 month follow up.

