### 3. Study procedure

*Figure 1. Flow chart of study procedures*

The study is conducted via Qualtrics, an online survey platform. A survey link will be emailed to participants for them to complete in their own environment. This allows the study to be completed anywhere. The survey will be live for 5 months of data collection before being taken offline. Participants will also be sent handouts of each week's intervention. After completing the screening questionnaire, eligible participants will be asked to fill in the FSDS-R, FSFI and SCSS. These questionnaires are filled in once weekly during phase A and B.

During Phase A which varies between 5- 14 days, participants will be sent Qualtrics links to where fill in visual analogue scales daily. The number of days' participants will be in baseline will be randomly allocated. There are 6 visual analogue scales that measure shame, guilt, self-criticism, self-compassion, normalising and motivation.

During phase B participants go through 1 module of the guided-self-help materials each week and complete the same visual analogue scales from baseline every day. After phase B. participants will be invited for a follow-up appointment one month after the intervention to fill in the FSDS, FSFI, SSCS-S client satisfaction questionnaire and feedback form developed with experts by experience.

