### **3.3 Statistical analysis of data**

Descriptive statistics will be completed for demographic information. Visual analysis will be performed for daily VAS ratings to evaluate the reliability of treatment effects between the baseline and treatment phases. To investigate if there is pre-and post-difference between scores a reliable change index (RCI) will be calculated for each measure using Jacobson & Traux (1991) to test if changes are statistically significant. Tau-U test will be used on outcomes to analyse non-overlap of intervention scores. Guidance and procedures will be followed from What Works Clearing House (Kratochwill et al., 2010).

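### The RCI pre-score is not defined; if it is the recruitment score, the RCI includes the untreated 5 to 14 day baseline, so one questionnaire set should be fixed at the end of phase A

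*Combined protocol and SAP*

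**What the plan says.** All references are to the combined protocol and SAP.

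- **Two-occasion schedule.** Section 2.3.3: "The FSDS-R is completed upon recruitment and at the 1 month follow up". Section 2.3.4: "The FSFI is completed upon recruitment and at the 1 month follow up". Section 2.3.5: "The SCSS-S is completed upon recruitment and at the 1 month follow up".
- **Order.** Section 2.1 puts the first completion at the eligibility and consent step: "Eligible participants will fill in questionnaires such as the FSDI, FSFI, SCSS-S, at this point". Phase A follows, "varying between 5- 14 days where they will fill in visual analogue scales daily". Section 2.2 also places this set at entry, after the screening call.
- **Weekly schedule.** Section 3, after describing the entry set, adds: "These questionnaires are filled in once weekly during phase A and B".
- **Treatment and follow-up.** Section 2.1 describes "phase B, which is a 4-week intervention period". Follow-up is one month after that.
- **Analysis.** Section 3.3: "To investigate if there is pre-and post-difference between scores a reliable change index (RCI) will be calculated for each measure". It ties neither the pre-score nor the post-score to an occasion. It also plans visual analysis of the daily visual analogue scales (VAS) across phases, and Tau-U on outcomes.
- **Role of the distress measure.** The secondary objectives in section 1.3 judge effectiveness by a reduction in measured sexual distress, together with better sexual satisfaction.

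**The concern.** Phase A exists so that change without the intervention can be seen and separated from change with it. An RCI that runs from recruitment to follow-up loses that separation, because drift during the untreated days is added to whatever happens afterwards.

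The daily VAS do not fill the gap. The six scales in section 2.3.2 cover shame, guilt, self-criticism, compassion, normalising and motivation. Some ask how the woman feels when she is distressed, but none rates the level of sexual distress. The outcome used to judge effectiveness is therefore the one for which baseline change may go unseen.

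The two schedules leave different problems. With two occasions, the recruitment score is the only possible pre-score. With weekly completion there are several candidates for both pre and post, and nothing prevents the choice being made after the data are seen.

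**Working it through.** The documents state no RCI cut-off, SD or reliability for the FSDS-R, so there is no figure of the plan's to reproduce. The numbers below are illustrations.

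**Inputs**
- Phase A is 5 to 14 days and phase B is 4 weeks, or 28 days (section 2.1).
- Follow-up is one month after phase B, taken as 30 days, with 28 to 31 as a range (assumption).
- Reliability r = .86. This is the alpha given for the SSCS-S in section 2.3.5 and the only coefficient stated for an RCI measure. Applying it to the FSDS-R is an assumption, so .70 to .95 is shown as a range.
- The cut-off is ±1.96 standard errors of the difference, with normal errors and no treatment effect (assumptions).

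**Step 1: share of the interval before module 1.** Share = A / (A + 28 + 30).
- A = 5: 5/63 = 7.9%.
- A = 14: 14/72 = 19.4%.
- With follow-up at 28 to 31 days, the extremes are 5/64 = 7.8% and 14/70 = 20.0%.
- If the post-score were instead taken at the end of phase B, the shares would be 5/33 = 15.2% and 14/42 = 33.3%.

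Any gap between the entry questionnaires and the start of phase A adds to these shares. The documents do not give its length.

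**Step 2: RCI cut-off.**
- Standard error of measurement = √(1 − .86) = 0.374 SD.
- Standard error of the difference = 0.374 × √2 = 0.529 SD.
- Cut-off = 1.96 × 0.529 = 1.04 SD (0.62 SD at r = .95, 1.52 SD at r = .70).

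**Step 3: effect of a fall before module 1.** Let d be the fall in SD units between entry and module 1. The chance of a false reliable improvement is 1 − Φ(1.96 − d/0.529). The last two columns use the standard errors for r = .70 and r = .95.

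| d (assumed) | r = .86 | r = .70 | r = .95 |
|---|---|---|---|
| 0 | 2.5% | 2.5% | 2.5% |
| 0.2 | 5.7% | 4.4% | 9.2% |
| 0.3 | 8.2% | 5.8% | 15.6% |
| 0.5 | 15.5% | 9.4% | 35.2% |

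At the minimum of 6 participants (section 2.2), assuming independence and r = .86, the chance of at least one false improver is:
- d = 0: 1 − 0.975⁶ = 14%.
- d = 0.3: 1 − 0.918⁶ = 40%.
- d = 0.5: 1 − 0.845⁶ = 64%.

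The expected number at d = 0.3 rises from 6 × 0.025 = 0.15 to 6 × 0.082 = 0.49.

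**Step 4: would the weekly schedule supply a later pre-score?** Not reliably.
- Completion on days 7 and 14 gives no phase A score for baselines of 5 or 6 days, one for 7 to 13 days, and two for 14 days.
- Completion on days 1 and 8 gives one for 5 to 7 days, but on day 1, so most of phase A stays inside the interval. It gives two for 8 to 14 days.

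A fixed rule for the end of phase A is needed under either schedule.

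**Step 5: what the fix does to the cut-off.** The last score before module 1 is still a single score, so the cut-off stays at 1.04 SD. With the mean of k pre-scores, √2 becomes √(1 + 1/k). For k = 2 the cut-off is 1.96 × 0.374 × √1.5 = 0.90 SD.

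**The case against.** Several stronger readings are tempting, and the documents do not support them.

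- **The plan has chosen the recruitment score as the pre-score.** A reader might infer this from sections 2.3.3 to 2.3.5, but section 3.3 names no occasion. If section 3 governs, phase A scores may exist and nothing fixes entry as the pre-score.
- **The FSDS-R RCI is the only analysis of change in distress.** That is so on the two-occasion schedule, which leaves no FSDS-R score inside either phase. On the weekly schedule Tau-U could also be run on the FSDS-R, though with few baseline points.
- **Entry scores sit at a help-seeking peak.** Nothing documents this. Section 2.2 recruits partly from waiting lists and partly through charities and social media, the assault must be more than 12 months past, and no FSDS-R threshold is used for entry. Women are selected for having sexual distress, so some fall towards the mean is plausible, but its size is unknown.
- **The RCI credits baseline change to the intervention.** An RCI tests only whether change exceeds measurement error; it does not attribute cause. Section 3.3 gives the phase comparison to the VAS, and effectiveness is a secondary, initial indicator.

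It is also fair to say that 81% to 92% of the interval lies after module 1 opens and stays uncontrolled whatever the pre-score, and that at 6 participants a 0.3 SD fall adds only about 0.34 expected false improvers.

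What stands is narrower. On the two-occasion schedule the RCI must span phase A; on the weekly one the pre-score is left open; and the VAS do not cover the level of distress. Because section 1.3 treats a fall in that measure as the sign of effectiveness, readers will draw the inference even though the RCI itself does not.

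**Conclusion.** The concern holds as a gap in definition with a possible bias, not as a demonstrated bias. The questionnaire timetable contradicts itself, section 3.3 does not say which scores enter the RCI, and the recruitment score would bring 5 to 14 untreated days into the interval.

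The interval share rests on the stated phase lengths and a 30-day month. The false-improvement rates rest on an assumed reliability, an assumed cut-off and assumed pre-treatment falls. They show sensitivity and do not predict what will happen in this trial. Reconciling the timetable alone would not settle the matter: keeping two occasions leaves the pre-score ahead of phase A, and keeping weekly ones leaves it unnamed. The point is worth acting on because the remedy is cheap and works whichever schedule is kept.

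**What to change.** 1. Reconcile sections 2.3.3 to 2.3.5 with section 3, so that there is one timetable for the FSDS-R, FSFI and SSCS-S.
2. Schedule one set of the three questionnaires on the last day of phase A, for every allocated baseline length.
3. In section 3.3, define the RCI pre-score as that last score before module 1 opens, and the post-score as the 1-month follow-up.
4. Report the change from entry to the end of phase A beside each RCI, so readers can see whether scores moved before treatment.
5. Optionally, as a sensitivity analysis, use the mean of all scores before module 1, with the standard error adjusted for the number averaged.

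The cost is some wording in section 3.3 and one moved or extra online questionnaire set per participant. Even under the weekly schedule, tying a set to each randomised baseline end is a real scheduling change. Moving the entry set instead of repeating it would lose the comparison in item 4. The fix takes phase A change out of the RCI, but it may not remove all the bias, since any temporary elevation at entry could outlast 5 to 14 days.
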